## 8. EARLY DISCONTINUATION

Subjects may choose to discontinue study drug or study participation at any time, for any reason, and without prejudice.

The following must be completed and documented in the source documents and CRFs for all subjects who discontinue the study early:

- The reason for early study discontinuation.
- Safety data should be obtained and will include the following:
  - Orthostatic vital signs (blood pressure, temperature, pulse and respiratory rate after a 3-min sitting period followed by blood pressure and pulse after a 2-min stand period), brief physical examination, clinical laboratory tests, ECG, use of concomitant medications, and adverse events.

## 9. ADVERSE EVENTS/SERIOUS ADVERSE EVENTS

### 9.1. ADVERSE EVENTS - DEFINITION

An adverse event (AE) is any undesirable event that occurs to a subject during a study, whether or not that event is considered study drug-related. Monitoring for AEs will start at dosing. Examples include:

- Any treatment-emergent signs and symptoms (events that are marked by a change from the subject's baseline/entry status [e.g., an increase in severity or frequency of pre-existing abnormality or disorder])
- All reactions from study drug, an overdose, abuse of drug, withdrawal phenomena, sensitivity or toxicity to study drug
- Apparently unrelated illnesses
- Injury or accidents (Note: if a medical condition is known to have caused the

injury or accident, the medical condition and the accident should be reported as two separate medical events [e.g., for a fall secondary to dizziness, both "dizziness" and "fall" should be recorded separately])

- Extensions or exacerbations of symptoms, subjective subject-reported events, new clinically significant abnormalities in clinical laboratory, physiological testing or physical examination

All AEs, whether or not related to the study drug, must be fully and completely documented on the AE page of the Case Report Form (CRF) and in the subject's clinical chart.

In the event that a subject is withdrawn from the study because of an AE, it must be recorded on the CRF as such. The subject should be followed and treated by the Investigator until the abnormal parameter or symptom has resolved or stabilized.

The Investigator must report all directly observed AEs and all spontaneously reported AEs. The Investigator will ask the subject a non-specific question (e.g., "Have you noticed anything different since your dose of the study medication?") to assess whether any AEs have been experienced since the last assessment. AEs will be identified and documented on the AE CRF in appropriate medical terminology. The severity and the relationship to the study drug will be determined and reported on the CRF (see below).

## **9.2. ADVERSE EVENTS - SEVERITY RATING**

The severity of each AE should be characterized and then classified into one of three clearly defined categories as follows:

- Mild - the AE does not interfere in a significant manner with the subject's normal functioning level. It may be an annoyance.
- Moderate - the AE produces some impairment of functioning, but is not hazardous to health. It is uncomfortable or an embarrassment.
- Severe - the AE produces significant impairment of functioning or incapacitation and is a definite hazard to the subject's health.

These three categories are based on the Investigator's clinical judgment, which in turn depends on consideration of various factors such as the subject's report, and the physician's observations. The severity of the AE should be recorded in the appropriate section of the Adverse Event CRF.

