#### **4.1 STOPPING CRITERIA**

Dose escalation will be suspended or stopped if any of the following occur and are potentially related to administration of the study drug:

- Clinical signs or symptoms of moderate intensity or greater in two or more subjects
- A single clinical sign or symptom of severe intensity
- AST/ALT elevation greater than 3x upper limit of normal
- Bilirubin elevation greater than 2x upper limit of normal
- Creatinine elevation greater than 1.5x upper limit of normal
- Any significant laboratory finding, confirmed by repeat laboratory testing

The DSMB/DMC may subsequently recommend a second sentinel group to proceed with planned protocol dosing, or termination of the study.

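### The Severe grade in Section 9.2 requires both impairment and hazard, so a single event with only one of the two need not meet a listed criterion for suspending escalation (modest effect, cheap to fix)

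*Combined protocol and SAP*

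**What the plan says.** Section 9.2 sets out three grades:

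- "Mild - the AE does not interfere in a significant manner with the subject's normal functioning level"
- "Moderate - the AE produces some impairment of functioning, but is not hazardous to health"
- "Severe - the AE produces significant impairment of functioning or incapacitation and is a definite hazard to the subject's health"

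It then leaves the choice of grade to the physician: "These three categories are based on the Investigator's clinical judgment".

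Section 4.1 is the written rule for escalation: "Dose escalation will be suspended or stopped if any of the following occur and are potentially related to administration of the study drug". Six criteria follow. Four are laboratory criteria (AST/ALT, bilirubin, creatinine, and any significant laboratory finding confirmed on repeat). The other two are "Clinical signs or symptoms of moderate intensity or greater in two or more subjects" and "A single clinical sign or symptom of severe intensity". Section 4.1 neither defines intensity nor cites Section 9.2.

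Section 9.1 counts as AEs "new clinically significant abnormalities in clinical laboratory, physiological testing or physical examination". Clinically significant ECG and vital-sign changes are therefore AEs, and Section 9.2 asks for each AE to be graded.

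**The concern.** The grade decides how many subjects it takes to suspend escalation. One Severe event is enough. A Moderate event also needs a second subject with a sign or symptom of at least moderate intensity. An event graded Mild, or fitting no grade, counts toward neither criterion.

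Because Severe needs impairment and hazard together, an event that is serious on one dimension alone can miss the single-event criterion. The example that matters most is an ECG or blood-pressure abnormality that is dangerous but leaves the volunteer feeling and functioning normally. In a first-in-human trial, such a sign in one subject should lead to a pause without anyone having to read past the written definitions.

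**Working it through.** The plan states no figure on this point, so there is none to reproduce. The check sets the definitions beside the escalation rule.

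**Inputs.** The three definitions come from Section 9.2 and the two intensity criteria from Section 4.1.

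**Assumptions.** Intensity in Section 4.1 means the Section 9.2 grade; the event is potentially drug-related; where two grades fit, the higher applies.

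**Step 1: the literal conditions.**

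- Severe = (significant impairment or incapacitation) AND definite hazard
- Moderate = some impairment AND no hazard
- Mild = no significant interference with functioning, whatever the hazard

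**Step 2: apply them to one event in one subject.** Three levels of impairment by hazard yes/no give 3 × 2 = 6 states.

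| Impairment | Hazard | Grade as written | One event meets 4.1? | Grade if Severe uses *or* | One event meets 4.1? |
|---|---|---|---|---|---|
| None or insignificant | No | Mild | No | Mild | No |
| None or insignificant | Yes | Mild at most | No | Severe | Yes |
| Some, not significant | No | Moderate | No | Moderate | No |
| Some, not significant | Yes | Not Moderate, not Severe | No | Severe | Yes |
| Significant or incapacitating | No | Moderate at most | No | Severe | Yes |
| Significant or incapacitating | Yes | Severe | Yes | Severe | Yes |

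As written, 1 of the 6 states meets the single-event criterion. With *or*, 4 of 6 do. These are counts of logical cases and not probabilities, since the states are not equally likely.

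**Step 3: consider two subjects.** Two incapacitating, non-hazardous events graded Moderate would meet the two-subject criterion. Two hazardous signs without significant impairment would not, because neither reaches Moderate as written.

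**Step 4: look for another listed criterion.** The remaining four concern laboratory values or findings. None names an ECG finding, a vital sign or an SAE.

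**The case against.** The strongest reply is that nobody grades AEs by truth table. Section 9.2 rests on clinical judgment, only Severe speaks of a definite hazard, Moderate rules hazard out, and Mild is illustrated as an annoyance. A physician choosing the best fit for a dangerous ECG change would probably choose Severe. This is fair, and it is the main reason the effect is modest. But that physician reaches the right answer by setting aside the impairment limb of the definition.

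There are also other safeguards:

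- Section 4 holds the remaining six subjects at every dose level until the DSMB/DMC has reviewed the sentinel pair's 24-hour ECG, physical examination, vital signs and laboratory data. That hold does not depend on any grade. As described, it covers the sentinel pair, and a second pair if concerns arise, but not every subject.
- Section 9.4 makes an AE suggesting a significant hazard an SAE and lists significant incapacity among SAE outcomes. Section 9.5 requires a report within 24 hours. An SAE is not a Section 4.1 criterion.
- The sponsor may stop at any time (Section 11), and the investigator may depart from the protocol to protect subjects (Section 13). Both are discretionary.

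The incapacitating but non-hazardous event is also hard to picture in practice. The hazardous sign without impairment is the more plausible case.

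A reader might infer three stronger things, none of which the documents support:

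- *That escalation would continue after a hazardous event.* The text shows only that no listed criterion need be met. The safeguards above could still halt dosing.
- *That a chance of a missed suspension can be calculated.* The documents give no event rate, and Section 4.1 does not say whether its two subjects are counted within a cohort or across cohorts.
- *That the blood-pressure rise in high-dose female dogs (Section 2) makes such a sign likely here.* It occurred in a 28-day study at 4,000 mg/m² per day, and 4,000 / 123 = 32.5 times the top single human dose. It resolved, and the dog cardiovascular study showed no adverse effect. It illustrates a type of sign and no more.

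**Conclusion.** The point holds as a modest wording defect. If intensity in Section 4.1 is the Section 9.2 grade, then one potentially related hazardous sign without significant impairment, or one incapacitating event without hazard, need not meet a listed criterion for suspending escalation. The link between the sections is inferred, though strongly, since Section 9.2 holds the only severity scale. The other assumption is that the definitions are applied as written.

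Investigator judgment, SAE reporting and sentinel review reduce the practical effect, but none is a listed suspension criterion covering all subjects. No probability is attached. Whether Section 4.1 should carry numeric ECG or vital-sign limits is a separate question that this point does not raise. The label is a cheap improvement.

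**What to change.** In Section 9.2:

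- **Severe:** replace the *and* between the impairment limb and the hazard limb with *or*, so that either is sufficient.
- **Mild:** add the no-hazard condition that Moderate already carries.
- Leave the impairment boundary between Mild and Moderate as it is. Nothing here shows a fault in it, and moving it would shift non-hazardous events into the two-subject criterion.

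In Section 4.1, state that intensity is the Section 9.2 grade and that this includes ECG and vital-sign abnormalities recorded as AEs.

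The cost is protocol wording and the matching CRF guidance. No threshold, procedure or subject is added. The downside is that escalation may be paused for DSMB/DMC review somewhat more often.

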## **9.3. ADVERSE EVENTS - RELATIONSHIP TO STUDY DRUG**

The relationship of each AE to the study drug will be classified into one of three defined categories as follows:

- Unlikely – a causal relationship between the AE and the study drug is

unlikely.

- Possible — a causal relationship between the AE and the study drug is possible.
- Probable – a causal relationship between the AE and the study drug is probable. For example, the AE is a common adverse event known to occur with the pharmacological class the study drug belongs to; or the AE abated on study drug discontinuation and reappeared upon rechallenge with the study drug

These three categories are based on the Investigator's clinical judgment, which in turn depends on consideration of various factors such as the subject's report, the timing of the AE in relationship to study drug administration/discontinuation, the physician's observations and the physician's prior experience. The relationship of the AE to the study drug will be recorded in the appropriate section of the Adverse Event CRF.

#### 9.4. SERIOUS ADVERSE EVENTS AND UNEXPECTED ADVERSE EVENTS - DEFINITIONS

Any AE that suggests a significant hazard, contraindication, side effect or precaution is defined as a Serious Adverse Event (SAE). An SAE includes (but is not limited to) an experience occurring at any dose that results in any of the following outcomes:

- Death
- A life-threatening event (i.e., the subject is at immediate risk of death from the reaction as it occurs). "Life-threatening" does not include an event that, had it occurred in a more serious form, might have caused death. For example, drug-induced hepatitis that resolved without evidence of hepatic failure would not be considered life-threatening even though drug-induced hepatitis can be fatal.
- In-patient hospitalization (hospital admission, not an emergency room visit) or prolongation of existing hospitalization.
- A persistent or significant disability/incapacity (i.e., a substantial disruption of the subject's ability to carry out normal life functions).
- A congenital anomaly/birth defect.

In addition, medical and scientific judgment should be exercised in deciding whether other situations should be considered an SAE (i.e., important medical events that may not be immediately life-threatening or result in death, but may jeopardize the subject or may require medical or surgical intervention to prevent one of the other outcomes listed in the definition above). Examples of such medical events include (but are not limited to): allergic bronchospasm requiring intensive treatment in an emergency room or at home, blood dyscrasias or convulsions that do not result in in-patient hospitalization, or the development of drug dependency or drug abuse.

An **unexpected** AE is one for which the specificity or severity is not consistent with the current Investigator's Brochure. For example, hepatic necrosis would be

unexpected (by virtue of greater severity) if the Investigator's Brochure only listed elevated hepatic enzymes or hepatitis.

Similarly, cerebral thromboembolism and cerebral vasculitis would be unexpected (by virtue of greater specificity) if the Investigator's Brochure only listed cerebral vascular accidents.

#### **9.5. SERIOUS ADVERSE EVENTS REPORTING**

The reporting of SAEs by the Sponsor to Regulatory Authorities (e.g., FDA) is a regulatory requirement. Each Regulatory Agency has established a timetable for reporting SAEs based upon established criteria. Likewise, it is the responsibility of the Principal Investigator to report SAEs to their EC/IRB.

All SAEs must be reported immediately (**within 24 h of learning of the event**) by telephone to:

[name], MD  
Pain Therapeutics, Inc.  
Email: [[contact]](mailto:[contact])  
[contact]

Do not delay reporting a suspected SAE to obtain additional information. Any additional information, if collected, can be reported to the Sponsor as a follow-up to the initial report.

A completed SAE report form must be faxed within five working days to the medical monitor. SAEs must also be reported to the responsible EC/IRB immediately.

In the case of a death or other SAE that has occurred within 30 days after receiving study drug, the Principal Investigator must also report such an event within 24 hours of being notified. Your local EC/IRB may also require these reports.

In the event of any SAE (other than death), the subject will be instructed to contact the study physician (Principal Investigator or designee) using the phone number provided in the Informed Consent Form. All subjects experiencing an SAE will be seen by a Principal Investigator or designee as soon as feasible following the report of an SAE.

## 10. STATISTICAL CONSIDERATIONS

### 10.1. RANDOMIZATION

Subjects will be assigned to PTI-125 or placebo based on a computer-generated randomization schedule prepared prior to the study. Pain Therapeutics, Inc. (PTI) will interact with the pharmacy to have study drug for each subject labeled according to this randomization code. Randomization Numbers will be used as subject code numbers and will be assigned when qualified subjects are randomized.

The randomization code will not be revealed to study subjects, investigators, clinical staff or study monitors until all subjects have completed therapy and the database has been finalized and closed.

Under normal circumstances, the blind should not be broken. The blind may be broken only if specific emergency treatment is indicated. The date, time and reason for the unblinding must be documented on the case report form, and the medical monitor must be informed as soon as possible.

### 10.2. ANALYSIS POPULATIONS

All subjects who receive study medication will be included in safety analyses. All subjects who have sufficient data for PK analysis will be included in the PK analysis population.

### 10.3. PHARMACOKINETIC PARAMETERS

PK parameters for PTI-125 will be calculated using non-compartmental methods in WinNonlin. The peak drug concentration ( $C_{max}$ ), the time to peak drug concentration ( $T_{max}$ ),  $T_{last}$  and  $C_{last}$ , the time to and concentration of the last quantifiable drug concentration, will be obtained directly from the data without interpolation. The following parameters will be calculated: the elimination rate constant ( $\lambda_z$ ), the terminal elimination half-life ( $T_{1/2}$ ), the AUC from time zero to the time of the last quantifiable concentration ( $AUC_{last}$ ), the AUC from time zero extrapolated to infinity ( $AUC_{inf}$ ), and the percentage of  $AUC_{inf}$  based on extrapolation ( $AUC_{extrap}(\%)$ ),  $Cl/F$ , the apparent oral clearance, and  $V_z/F$ , apparent volume of distribution.

In the pharmacokinetic analysis, BLQ concentrations will be treated as zero from time-zero up to the time at which the first quantifiable concentration was observed; embedded and/or terminal BLQ concentrations will be treated as "missing". Full precision concentration data (not rounded to three significant figures) and actual sample times will be used for all pharmacokinetic and statistical analyses. Nominal sampling times will be used to prepare concentration versus time profiles.

#### **10.4. STATISTICAL ANALYSIS**

Comparison of the PK parameters  $C_{max}$ ,  $AUC_{last}$ , and  $AUC_{inf}$  for PTI-125 between treatments will be done using an analysis of variance (ANOVA) model with factors for period and treatment.  $T_{max}$  will be compared among groups using a non-parametric analysis (Wilcoxon Rank Sum or Signed Ranks tests).

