A robust nonclinical ADME, safety pharmacology, and general and genetic toxicology program has been carried out with PTI-125. In vitro metabolic profiling showed minimal metabolism across several species and in man. PTI-125 was rapidly absorbed and eliminated in in vivo studies in rat and dog with nearly 100% oral bioavailability, a 2.67-h half-life in dog, dose proportional PK and no accumulation. Safety pharmacology studies showed no adverse effects on gross behavioral and physiological parameters in the Irwin test of CNS toxicity in rats, no adverse effects on respiratory rate, tidal volume or minute volume in the rat respiratory test, and no adverse effects on arterial blood pressure, heart rate and ECG parameters in the dog cardiovascular study. The in vitro hERG test for cardiotoxicity also indicated no adverse effect. A full battery of genotoxicity studies was conducted (in vitro bacterial Ames, in vitro chromosomal aberration, and in vivo rat micronucleus test) and were all negative. An in vitro specificity screen showed no significant activation or inhibition of a panel of 67 receptors, channels and transporters.

PTI-125 was tested in single dose and repeat dose oral general toxicity studies in rats and dogs. In a 28-day repeat dose oral general toxicity study followed by a 28-day drug-free recovery period in rats, with PTI-125 dose levels up to and including 1000 mg/kg/day (equivalent to 6,000 mg/m^2), toxicity was mainly characterized at 1000 mg/kg/day by a decrease in mean body weight which continued during the recovery period. A diffuse cellular hypertrophy of the liver was seen at 1000 mg/kg/day in males and females and was interpreted as an adaptive response to the test article. There were no other adverse effects and all biologically significant findings noted during the dosing period were resolved at the end of the 28-day recovery period. A no-observed-effect-level (NOEL) could not be determined and the no-observed-adverse-effect-level (NOAEL) was determined to be 500 mg/kg/day (equivalent to 3,000 mg/m^2).

A 28-day repeat dose oral general toxicity study in dogs, followed by a 28-day drug-free recovery period, with PTI-125 dose levels up to and including 200 mg/kg/day (equivalent

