### 4. SUMMARY OF STUDY DESIGN

This is a Phase I, single center, randomized, double-blind, placebo-controlled, SAD study of three escalating doses of PTI-125 in healthy male and female volunteers, 18-45 years of age. A total of twenty-four (24) subjects will be enrolled into the study in one of three dose cohorts. Each cohort will contain 8 subjects; six (6) subjects will receive PTI-125 and two (2) will receive placebo in each cohort. Three single ascending doses of PTI-125 oral solution (50, 100, and 200 mg) or placebo solution will be administered to respective cohorts.

The study includes a screening period (Day -28 to Day -1) and an inpatient treatment period (Day 0 through Day 4) and a follow-up visit (Day 7). Subjects will report to clinic the day before dosing and will be randomized to receive either a single dose of orally administered PTI-125 or placebo. Each dose will be administered following an overnight fast of 10 h.

For each dose level, dosing will be staggered such that 2 subjects (one active and one placebo) will be dosed prior to the rest of the group. After a minimum of 24 h and review of all 24-h safety assessments (ECG, brief physical, vital signs and laboratory

---

 Guidance for Industry: Estimating the Maximum Safe Starting Dose in Initial Clinical Trials for Therapeutics in Adult Healthy Volunteers. FDA, CDER, July 2005.

assessments) an independent Data Safety Monitoring Board/Data Monitoring Committee (DSMB/DMC) will determine whether the remaining 6 subjects will be dosed. If safety concerns are raised, 2 additional subjects (randomized according to the Rand schedule to maintain blinding) will be dosed followed by collection and review of the 24-hour safety assessments. The DSMB/DMC will determine after review if dosing will proceed for the remaining 4 subjects.

PK blood samples will be obtained prior to dosing and at specified intervals during the study (0-72 h post-dose). PK parameters will be calculated using non-compartmental analysis.

Blood draws for laboratory testing will be performed prior to dosing and at 24 h post-dose. After safety assessments of ECG, vital signs and a brief physical exam at 72 h, subjects will be discharged from the clinic and will return 7 days post-dose for a final safety assessment.

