#### **10.6. SAMPLE SIZE**

24 subjects will be enrolled in this study. Sample size was determined by estimating the intrasubject variability for log-transformed data from previous studies of new chemical entities (NCEs).

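### Section 10.4 compares Cmax and AUC between dose cohorts with no dose adjustment and no stated scale, so the test says little about whether exposure is proportional to dose

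*Combined protocol and SAP*

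**What the plan says.** Section 10.4 is the whole plan for comparing PK. For Cmax, AUClast and AUCinf, the comparison "for PTI-125 between treatments will be done using an analysis of variance (ANOVA) model with factors for period and treatment". Tmax gets rank tests. The section mentions no dose-normalisation, scale, power model, ratio, contrast or confidence interval.

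Section 4 fixes what the treatments are: "Three single ascending doses of PTI-125 oral solution (50, 100, and 200 mg) or placebo solution will be administered to respective cohorts". In each cohort, "six (6) subjects will receive PTI-125 and two (2) will receive placebo in each cohort", and each subject receives one dose. Section 7.2.2 has every sample from active subjects assayed but only one sample, near Cmax, from each placebo subject. So the only treatments with a PK profile are the three dose levels, with 6 subjects each.

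Three other places bear on the point:
- Section 10.6 bases the sample size on "estimating the intrasubject variability for log-transformed data". This is the only mention of a log scale.
- Section 10.3 derives CL/F, which takes account of dose, but section 10.4 does not list it for comparison.
- Section 2 reports "dose proportional PK and no accumulation" in rat and dog. Section 3 names safety and pharmacokinetics as what the study is to determine, without mentioning proportionality.

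**The concern.** With no dose adjustment, the null hypothesis of the ANOVA is that 50, 100 and 200 mg give the same exposure. Nobody expects that over a four-fold dose range. The usual PK question in an ascending-dose study is whether exposure rises in step with dose, faster or slower. A significant treatment effect is compatible with all three.

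PK is one of the two things the study sets out to determine. As planned, its only inferential comparison of Cmax and AUC would put in the report a p-value that carries almost no PK information. The animal finding of proportional PK would have no planned human follow-up.

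The silence on scale is a second, smaller matter. If the CV is roughly constant, the unlogged SD at 200 mg is about four times that at 50 mg, and a pooled error variance then fits no pair of doses.

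**Working it through.** **The plan's own figure.** 3 cohorts x (6 + 2) = 24 agrees with section 10.6 as a head count. It cannot be derived statistically, because no CV, effect size, alpha or power is given.

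**Inputs from the documents.** Doses of 50, 100 and 200 mg (1:2:4), and 6 active subjects per dose, 18 in all (section 4).

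**Assumptions.** Two-sided 5% test; between-subject CV of 20 to 60%; log-normal data with SD on the log scale σ = √ln(1 + CV²), which is 0.198, 0.294, 0.472 and 0.555 at CV 20, 30, 50 and 60%; exposure proportional to dose^b. Over the four-fold range, b = 0.7 means a 4^0.7 = 2.6-fold rise in exposure and b = 1.3 means a 4^1.3 = 6.1-fold rise. The period factor is dropped, because each subject has one dose in one cohort. That leaves a one-way ANOVA on 2 and 15 df.

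**Rejection rates of the treatment test (50,000 simulated trials per setting).**

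| Analysis | True slope b | CV 20% | CV 30% | CV 50% | CV 60% |
|---|---|---|---|---|---|
| Unlogged, not dose-normalised | 0.7 | 100% | 99.5% | 74% | 57% |
| | 1.0 | 100% | 100% | 95% | 85% |
| | 1.3 | 100% | 100% | 99% | 96% |
| Logged, not dose-normalised | 1.0 | 100% | 100% | 99% | 95% |
| Logged and dose-normalised | 0.7 | 85% | 50% | 21% | 17% |
| | 1.0 | 5% | 5% | 5% | 5% |
| | 1.3 | 84% | 50% | 22% | 17% |

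The logged row can be checked exactly. The noncentrality is 12(ln 2)²/σ² = 5.765/σ². At CV 50%, σ² = ln 1.25 = 0.223 and the noncentrality is 25.8, which gives 98.8% from the noncentral F distribution, as simulated.

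**Reading the table.** Without dose-normalisation, rejection does not tell proportional from non-proportional PK. At CV 30% it is 100/99.5 = 1.005 times as likely under b = 1.0 as under b = 0.7. Even at CV 60% the ratio is only 85/57 = 1.5. Only the dose-normalised test holds its 5% level when exposure is proportional and rises above it when it is not. The missing dose adjustment is therefore the main fault, and logging alone does not cure it.

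**If the analysis were run unlogged with pooled-variance intervals.** Let v be the variance at 50 mg. With constant CV and proportional exposure, the variances are v, 4v and 16v, and the pooled variance is 21v/3 = 7v.
- 100 vs 50 mg: the true variance of the difference is (1 + 4)v/6 = 0.83v, against 14v/6 = 2.33v assumed. The standard error is √(2.33/0.83) = 1.67 times too large.
- 200 vs 100 mg: the true variance is (4 + 16)v/6 = 3.33v, against 2.33v assumed. The standard error is √(2.33/3.33) = 0.84 of what it should be.

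In simulation at CV 30%, nominal 95% intervals cover about 99% and 89% respectively.

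**What a power model would give.** The sum of squares of ln(dose) is 6 x 2 x (ln 2)² = 5.765, with square root 2.401. The slope SE is σ/2.401, and the 90% CI half-width is t(0.95; 16 df) = 1.746 times that.
- CV 20%: 1.746 x 0.198/2.401 = 0.14
- CV 30%: 1.746 x 0.294/2.401 = 0.21
- CV 50%: 1.746 x 0.472/2.401 = 0.34

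**The case against.** The other side has a good deal to say, and four stronger readings that a reader might draw should be set aside.

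- *That the protocol specifies an analysis of raw values.* It does not. Section 10.4 is silent on scale, and section 10.6 speaks of log-transformed data, so a log analysis may have been intended. The coverage figures apply only if it was not. The dose-adjustment point stands on either scale.
- *That the protocol's confidence intervals are miscalibrated.* Section 10.4 plans no intervals or pairwise contrasts. The 99% and 89% describe what would follow if such intervals were produced from an unlogged pooled ANOVA.
- *That significance is certain whatever the PK.* This depends on a CV that the documents do not give. At b = 0.7 the unlogged test rejects in 74% of trials at CV 50% and 57% at CV 60%. What survives is that rejection does not indicate proportionality at any CV examined. Non-rejection would not separate a shallow slope from high variability.
- *That a stated aim fails, or that the study cannot show proportionality.* Proportionality is not a named objective, and the animal result is background. CL/F is derived for active subjects and can be inspected by dose, and no data are lost. But section 10.4 plans no such comparison, so it would be chosen after the data were seen.

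The rejection rates also describe a repaired model. Section 10.4 as written includes a period factor that this parallel-cohort design cannot support. That is a separate fault in the same sentence, and correcting it leaves this one in place.

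Finally, the fix adds only modest information. With 6 subjects per dose, a two-sided 5% test of slope 1 detects a true slope of 0.8 or 1.2 with about 34% power at CV 30%. That is a reason to report an estimate, not a reason to keep an uninformative test.

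**Conclusion.** The concern holds in this limited form: the planned comparison of Cmax and AUC has no dose adjustment and no stated scale, so it mainly confirms that more drug gives more exposure. No informative PK comparison is planned, although PK is one of the two objectives.

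The size rests on an assumed CV and alpha, log-normal data and a one-way model. On those terms the treatment test rejects in 85 to 100% of trials under exact proportionality across CV 20-60%, and in 57 to 100% at slope 0.7.

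The change should be made. Subject safety is not affected, and no data would be lost if it were made late. Its value lies in stating the analysis before the results are known.

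**What to change.** In section 10.4:

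1. State that Cmax, AUClast and AUCinf are analysed on the natural-log scale.
2. Make the main PK summary a power model, ln(parameter) = a + b·ln(dose), reporting b with its 90% CI for each parameter.
3. Support it with geometric mean ratios and 90% CIs between doses from log dose-normalised values. For AUCinf this is equivalent to comparing log CL/F, since CL/F = dose/AUCinf.
4. Label these results as estimation, with no pass/fail criterion for proportionality.
5. Make the edit together with the separate correction of the period factor and the signed-rank option, which belong to a crossover design.

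The cost is protocol or SAP wording and a few lines of code, with no new subjects, samples or visits. The drawback is a wide slope interval, as shown above, and the text should say so in advance.
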